**Official title: A Comparison of Epidural and Intravenous
Patient Control Analgesia Following Lumbar Spinal Fusion
Surgery: A Prospective Randomized Study**

NCT number: NCT03115151

IRB Approved date: 03-28-2022

**The University of Texas Southwestern Medical Center at Dallas
Institutional Review Board**

Protocol

Title: A Comparison of Epidural and Intravenous Patient Control Analgesia Following Lumbar Spinal Fusion Surgery: A Prospective Randomized Study

Funding Source: Departments of Anesthesiology & Pain Management and Neurosurgery; University of Texas Southwestern, Dallas, Texas

Principle Investigator:

- [name], MSc; Assistant Professor of Anesthesiology & Pain Management

Co- Principle Investigator:

- [name]; Associate Professor of Neurosurgery

1. Introduction and Purpose – Postoperative analgesia following spine surgery is difficult to manage. Current treatment modalities rely heavily on opioid analgesics with all of the inherent limitations and side effects. While current best practice focuses on a ‘multimodal approach’ (i.e. using multiple different drugs and techniques to control pain after surgery), there is no consensus regarding which components of this multimodal therapy provide optimal analgesia. This prospective randomized study will enroll patients undergoing elective Lumbar Spinal Fusion Surgery at Zale Lipshy University Hospital. The primary objective is to determine the comparative efficacy of epidural analgesia, as compared with intravenous (IV) patient-controlled analgesia (PCA), on post-operative analgesia.

Hypothesis1: We hypothesize that patients undergoing Lumbar Spinal Fusion surgery with epidural catheter placement will have superior post-operative analgesia compared to patients receiving IV PCA.

Specific Aim1: Patient received PCEA will have lower Visual Analog pain scores (VAS) at 24 hour postoperatively compared to those who received IV PCA.

Primary outcome measure: Postoperative VAS score at 24 hours

Hypothesis2: Epidural analgesia with intraoperative epidural catheter may decrease postoperative opioid consumption compared to IV PCA.

Specific Aim2: Patients received PCEA with intraoperative epidural catheter will consume less opioid during the first 24-h postoperative period compared to those who received IV PCA.

Secondary outcome measure: Postoperative opioid consumption within the first 24 hours.

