2. Background & Significance – Low back pain is one of the most prevalent debilitating musculoskeletal conditions in the United States. (1) Therefore, lumbar spine surgery is a commonly performed procedure in the United States. Many patients undergoing lumbar spine surgery have chronic pain syndromes pre-operatively which can present challenges in the treatment of post-operative pain. The importance of adequate post-operative pain control has recently been emphasized with the awareness that inadequate treatment may result in a higher incidence of the development of chronic post-surgical pain and increase post-operative comorbidities. (2) Multiple drugs and protocols for the treatment of post-operative pain

STU092016-061, [name], FormA-ResearchProtocol, Mod_24, 03-28-22

following lumbar spine surgery have been studied, but no best method has been shown to date. (3)

Most studies of lumbar spine surgery pain management have investigated comparisons between intravenous opioids, intrathecal local anesthetics and opioids, and epidural local anesthetics and opioids. There have been mixed results regarding the superior approach to post-operative pain management and complications. (4-7) Several of these conflicting studies contain small sample sizes and have various other limitations. Therefore, further investigation is warranted to improve post-operative pain control following lumbar spine surgery. The current study seeks to improve care of patients in the UT Southwestern Spine Center by comparing intravenous patient-controlled opioid analgesia versus continuous epidural analgesia. There are several potential advantages to epidural therapy. These include decreased opioid use leading to fewer side effects such as respiratory depression, nausea, ileus, and sedation. (8) Epidural analgesia has also been shown to provide better post-operative analgesia when compared to parenteral opioids in a variety of surgical procedures and with a variety of analgesic agents. (2)

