1. 29 subjects receiving Continuous Lumbar Epidural Analgesia (Patient-Controlled Epidural Analgesia- PCEA groups)
2. 29 subjects receiving IV PCA

Subjects will be randomly assigned one of the study groups either PCEA or IV PCA. Randomization protocol will be prepared according to level of the spinal fusion levels (1-3).

Study Interventions – The intervention to be evaluated in this study is epidural analgesia using an infusion of 0.0625% bupivacaine plus fentanyl 2mcg/ml. The Patient Controlled Epidural Analgesia (PCEA) pump will be programmed with the following settings:

- Bolus dose 5ml following emergence from general anesthesia (after clinical neurologic exam)
- Infusion 6-10 ml/hour; 2ml demand bolus every 20 minutes
- Max dose set for infusion over 4 hours + 6 boluses (12ml)
(Example - infusion 5ml/hr.; max 32ml over 4 hours)

This infusion will continue into the post-operative period. The epidural infusion will be continued until it is appropriate to transition the patient to a regimen of oral pain medications. This is typically determined by the surgical team, and the Acute Pain Service (APS). Duration of epidural catheter will be 72 hours a postoperatively. The APS will discontinue the epidural infusion and remove the epidural catheter per standard protocol.

For subjects in the IV PCA group, the intervention will include post-operative IV PCA with Hydromorphone (PCA syringe 25 mg/50 mL; dose range is 0.05mg - 0.4 mg which may be change according to patient's body habitus, age, etc.).

Epidural catheters will be placed by the spine surgeon under direct visualization intra-operatively prior to closing the surgical incision. Intra-operative epidural catheter placement by the spine surgeon will typically be done at the upper end of the dural exposure/laminectomy and the catheter will be pushed cephalad 5-10cm up the epidural space. For safety reasons, the subjects with dura damage during surgery will be excluded from the study because unpredictable amounts of the local anesthetic might reach the intrathecal space.

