Epidurals will be assessed for efficacy/function in the recovery room post-operatively by the APS, and then daily on the floor post-operatively (unless contacted by the floor nurse regarding specific concerns). Subjects are assessed for sensory function provided by the epidural (typically by sensation to cold or sharp), motor function, and any side effects or complications from the epidural. Motor block will be quantified with the Bromage scale (0 _ free movements of legs and feet, 1 _ just able to flex the knees with free movement of the feet, 2 _ unable to flex the knees but with free movement of the feet, and 3 _ unable to move legs or feet). Subjects will be asked about sensory deficits and graded on scale 1 to 3 (1 intact sensation, 2_ partial sensation, and 3_ complete sensation lost).

Visual analog pain scale (VAS) will be used to evaluate degree of pain at, 24, 48, and 72 hours after surgery. If a subject reports inadequate pain control with an epidural and the APS deems the epidural to be non-functional or non-efficacious, then the catheter may be removed and the patient may be changed to an IV PCA at that time.

Additionally, both the IV PCA and the epidural PCEA groups may be given additional “rescue” pain medications as needed in the recovery room, and these may be continued through the post-operative period on the floor. Current standard of care is using multimodal analgesia including acetaminophen, COX-2 specific inhibitors, dexamethasone, etc. These rescue medications may include, but are not limited to: pregabalin, gabapentin, methocarbamol, oxycodone, hydrocodone, methadone, and acetaminophen.

Total study duration is approximately 50 days, which starts from operating room admission for spinal fusion surgery to the first follow-up visit after discharge. Postoperative data will be collected during hospital stay and at the first follow-up visit.

4. Study Procedures:

Monitoring:

Standard intraoperative monitoring (EKG, blood pressure, pulse oximetry, end-tidal carbon dioxide, and temperature) and anesthetic care will be used in both groups.

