Surgical and anesthetic technique: All subjects will undergo a standardized general anesthetic for the operative procedure (see Appendix 1). The surgery and postoperative management will also be standardized. The difference between patient cohorts will be the use of epidural vs. intravenous analgesia for post-operative pain management. Both study groups will receive hydromorphone, which is a standard of care drug for post-operative pain. If the subject has a documented allergy or intolerance to hydromorphone, then a different opioid may be substituted in either the IV PCA or the epidural drug solution. The epidural study group will also receive Bupivacaine (local anesthetic) in combination with fentanyl. The intervention being tested in the current study is the route of analgesic medication—intravenous or epidural,

as well as the addition of bupivacaine in the epidural analgesic group. Note that bupivacaine contraindicated for intravenous use, and may have significant cardiac and neurologic sequelae if given intravenously. Therefore, it will be included only in the epidural analgesia group.

Epidurals that are evaluated and felt to be non-efficacious will be removed, and the subject will be changed to intravenous hydromorphone PCA. These subjects will be statistically analyzed primarily by intent to treat method, with possible secondary analysis, to be analyzed in an 'as treated group'. Investigators will not be blinded to treatment allocation due to the nature of the intervention. Subjects will be randomized to receive IV PCA or epidural PCEA.

The following **variables** will be evaluated to determine differences between Epidural Analgesia and Standard Care:

Preoperative Data Collection during preoperative outpatient clinic visit or preoperative period before the surgery

- VAS score
- Baseline delirium assessment (the Confusion Assessment Method (CAM) and the Mini-Cognition assessment (MiniCog)
- Hospital anxiety depression scores (HADS) will be evaluated- baseline (preop)
- Pain will also be evaluated with McGill short form questionnaire-baseline (preop).

Postoperative data collection during hospital stay:

- Post-operative Visual Analogue Pain (VAS) Score within 3 hours or PACU discharge, postoperative 24, 48, and 72 hours during infusion days (± 2 hrs.) after surgery (Primary endpoint: VAS Score at 24h).
- Post-operative intravenous opioid consumption for postoperative days 1, 2, and 3 (converted to Morphine Equivalents).

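### Hypothesis 2 claims less opioid in the first 24 hours without naming a route, and the PCEA arm's epidural fentanyl is not listed as study data

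*Combined protocol and SAP*

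**What the plan says.** Section 1 (Introduction and Purpose) gives "Secondary outcome measure: Postoperative opioid consumption within the first 24 hours". Specific Aim 2 gives the direction: PCEA patients "will consume less opioid during the first 24-h postoperative period compared to those who received IV PCA". Neither names a route. Section 2 (Background & Significance) explains why the outcome matters. Of the advantages of epidural therapy it writes "These include decreased opioid use leading to fewer side effects such as respiratory depression, nausea, ileus, and sedation".

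The epidural treatment itself contains an opioid. Section 3 (Study Interventions) describes "epidural analgesia using an infusion of 0.0625% bupivacaine plus fentanyl 2mcg/ml", delivered as a 5 ml bolus after emergence and then "Infusion 6-10 ml/hour; 2ml demand bolus every 20 minutes", with the limit "Max dose set for infusion over 4 hours + 6 boluses (12ml". If the epidural does not work, "then the catheter may be removed and the patient may be changed to an IV PCA at that time".

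The data to be collected are narrower than the hypothesis. Section 4 (Study Procedures) lists "Post-operative intravenous opioid consumption for postoperative days 1, 2, and 3 (converted to Morphine Equivalents". It ties oral opioid and breakthrough medication to postoperative day 3. Section 7 (Sources of Research Material) names intravenous and oral opioid only. Section 14 (Biostatistics) does not define the opioid outcome, combine routes or give a conversion factor.

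**The concern.** The control arm's assigned opioid is intravenous hydromorphone, which the listed variables count. The epidural arm's assigned opioid is fentanyl in the pump solution, which no listed variable counts. A lower 24-hour figure in the PCEA arm could therefore mean that these patients received less opioid, or only that part of their opioid went in by a route outside the tally. The listed data would not separate the two.

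Apart from the primary VAS score, this is the only outcome with its own hypothesis and aim, and it carries the opioid-sparing argument of section 2. The stake is limited to that claim: opioid side effects are collected directly in section 4, and the primary outcome does not use opioid data.

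**Working it through.** **The plan's own figures.** The documents give no figure for the opioid outcome. Two related figures reproduce.
- Four-hour limit in the section 3 example: 5 ml/h × 4 h + 6 × 2 ml = 20 + 12 = 32 ml, as stated. This confirms the reading of the limit as infusion plus at most 12 ml of demand boluses per 4 hours.
- Sample size in section 14 (VAS only): for d = 0.8, one-sided 0.025 and 80% power, the two-sample t-test needs 25.5, so 26 per arm and 52 in total; 52 / 0.9 = 57.8, so 58. This point does not touch it.

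**Routes given against routes listed.**

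| Opioid | Who receives it | Listed for the first 24 h? |
|---|---|---|
| IV hydromorphone by PCA (section 3) | IV PCA arm; PCEA patients after conversion | Yes, as IV opioid by postoperative day |
| Oral opioid and breakthrough medication (section 3) | Both arms | Listed, but tied to postoperative day 3; no 24-hour total specified |
| Epidural fentanyl (sections 3 and 4) | PCEA arm | No |
| Hydromorphone for both groups (section 4) | PCEA arm, route not given | Yes if intravenous; no if epidural |

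The epidural checks in sections 3 and 4 cover function, sensory and motor status and complications, not volume or dose. The medication list in section 7 stands with medical history and is not a dose record.

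**Amount of fentanyl not listed.** Inputs from section 3: 2 mcg/ml; 5 ml initial bolus (assumed to be the same solution); infusion 6-10 ml/h; demand boluses at most 12 ml per 4 h.
- Infusion volume over 24 h: 6 × 24 = 144 ml to 10 × 24 = 240 ml.
- Demand volume over 24 h: 0 to 12 × 6 = 72 ml.
- Lowest: 2 × (5 + 144 + 0) = 298 mcg.
- Highest: 2 × (5 + 240 + 72) = 634 mcg.
- At the 5 ml/h of section 3's own example: 2 × (5 + 120 + 0) = 250 mcg, up to 2 × (5 + 120 + 72) = 394 mcg.

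These are amounts for an epidural that runs the full 24 hours. A patient converted to IV PCA receives less; one converted straight after the initial bolus would have received 5 × 2 = 10 mcg.

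**Direction.** Let S be intravenous plus oral opioid and E epidural opioid, so that total opioid is S + E. In the IV PCA arm E = 0. The difference in S (PCEA minus IV PCA) equals the difference in total opioid minus the mean of E in the PCEA arm. Since E cannot be negative, leaving it out can only move the difference toward Hypothesis 2. If the outcome is S itself, leaving out E changes nothing.

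**Size in morphine equivalents.** The documents give no factor. Under an assumed range of 10 to 100 mcg of fentanyl per mg of IV morphine, 298 / 100 = 3.0 mg and 634 / 10 = 63.4 mg, about a 21-fold span. That span is a reason to give no size.

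**The case against.** The best reply is that systemic opioid is what the plan means. Section 4 introduces its list as the variables used to compare the arms, and that list says intravenous; section 7 says intravenous and oral; nothing promises an all-route total. On that reading the omission causes no bias. This stands as the reading that best fits sections 4 and 7. It does not settle the matter, because the hypothesis, the aim and the named outcome in section 1 carry no such limit. Even as a systemic outcome, the contrast partly reflects assigned route: one arm's study opioid is counted and the other's is left out.

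A reader might infer more than the documents support:
- *That the epidural dose is not recorded and cannot be recovered.* The documents show only that it is not listed as study data. A programmed pump delivers it and the Acute Pain Service reviews patients daily; whether delivered volume is charted is not stated.
- *That the tally misses all of the PCEA arm's planned opioid.* Section 4 says that both groups receive hydromorphone. Any given intravenously would be counted.
- *That the 24-hour window is undefined.* Aim 2 sets the first 24 hours, and the VAS times are counted from surgery. What is missing is an explicit time zero for opioid counting. The day-3 wording for oral and breakthrough use leaves a separate gap of unknown direction.

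**Conclusion.** The point holds as a mismatch between an unqualified claim and route-limited data, and it should be fixed. As written, the plan cannot support a statement that PCEA patients consumed less opioid.

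The outcome is not shown to be biased outright: that depends on which reading was intended. On the total-opioid reading, the direction of the omission is certain and favours Hypothesis 2. The amount left out is 298-634 mcg of fentanyl per patient with a full 24 hours of infusion, or from 250 mcg at the example rate, assuming that the initial bolus is the same solution and the stated limits are followed. The effect on a morphine-equivalent comparison cannot be fixed. On the systemic reading, bias from this omission is zero and the fault is in the label and the claim. If the PCEA arm's hydromorphone were epidural, the fentanyl figure would not be the whole of what is left out.

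One secondary outcome is affected. The primary VAS analysis and N = 58 are not.

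**What to change.** - Name the secondary outcome, Aim 2 and Hypothesis 2 as systemic (intravenous plus oral) opioid over 0-24 h from a stated time zero, and collect oral opioid for that same window.
- List epidural opioid, taken from delivered pump volume, as study data, and report it in mcg beside the systemic figure. This needs no epidural conversion factor.
- Do not claim lower total opioid from systemic data alone. An all-route total may be added as a sensitivity analysis with a prespecified range of epidural conversion factors.
- Reconcile the passages that decide which opioid is counted. Section 4 says that both groups receive hydromorphone, with no route for the PCEA arm, and allows another opioid to replace it in the IV PCA or the epidural solution. Section 3 gives the epidural solution as bupivacaine with fentanyl, and section 6 excludes hydromorphone allergy in patients assigned IV PCA. Section 3's 6-10 ml/h range must also be reconciled with its 5 ml/h example.

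The cost is outcome wording, one data-form line and a little abstraction of pump volumes. The sponsor gives up a total-opioid claim as the main result, and the opioid-sparing figure may look less favourable to PCEA. No patients or visits are added.

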- Total use of post-operative oral opioid consumption during hospital stay on postoperative day 3.
- Total use of breakthrough medication on postoperative day 3.
- Patient satisfaction score at the last infusion day or postoperative day 3 or at discharge if patient discharged before POD3.
- Delirium during the hospital stay. Patients will be assessed baseline (preop) and daily during epidural or IV infusion , and the 6-week follow-up using the Confusion Assessment Method (CAM) and the Mini-Cognition assessment.
- Epidurals will be assessed for efficacy/function in the recovery room post-operatively by the Acute Pain Service, and then daily during infusion days (24, 48, and 72 hours)
- Length of hospital stay.
- Nausea, vomiting and antiemetic use for postoperative 72 hours
- Time to first bowel movement after surgery
- Wound infection rates during hospital stay
- Time to first ambulation after surgery
- Adverse effects include nausea, vomiting, pruritus, drowsiness, respiratory depression, and headache etc.

Data collection during 6-week follow-up visit (approximately postoperative 50 days):

- VAS Score

- HADS
- Pain evaluation with McGill short form questionnaire
- Patient satisfaction with post-operative analgesia
- Readmission rates within 30 days of surgery
- Wound infection rates until the first follow up visit

5. Criteria for Inclusion of Subjects:

- Adult subjects aged 18 years or older
- Scheduled for elective posterior lumbar spinal fusion surgery between 1 and 3 levels

6. Criteria for Exclusion: Patients will be excluded if they have:

- Baseline cognitive deficits sufficient to make objective pain self-assessments unreliable in the estimation of the Study Investigators.
- Immunocompromised subject
- Coagulopathy
- Severe liver and renal dysfunction
- Preoperative neurological deficits
- The dura damage during surgery
- Inability to follow directions or comprehend the English language.
- Females who are pregnant
- Prisoners.
- Patient refusal to provide informed consent.
 - Allergy to amide local anesthetics (lidocaine, bupivacaine, ropivacaine) Fentanyl allergy if the subject assigned epidural analgesia
 - Hydromorphone allergy if the subject assigned IV PCA

7. Sources of Research Material

- Patient information including name, medical record number, Date of Birth, and contact information including phone number.
- Weight, height, BMI, medical and surgical history, Medication list
- Pain Scores

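### In-hospital delirium checks last only as long as the infusion, whose length belongs to the randomised treatment and is not fixed, so the arms could be checked unequally

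*Combined protocol and SAP*

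**What the plan says.** Section 4 of the protocol, under postoperative data collection during the hospital stay, names the outcome as delirium over the hospital stay and gives its schedule: "Patients will be assessed baseline (preop) and daily during epidural or IV infusion". It adds one later check, at "the 6-week follow-up using the Confusion Assessment Method (CAM) and the Mini-Cognition assessment". No CAM or Mini-Cog is scheduled between the end of the infusion and discharge.

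Section 3, under Study Interventions, describes the length of the epidural in two ways. One is fixed: "Duration of epidural catheter will be 72 hours a postoperatively". The other depends on clinical judgement: "The epidural infusion will be continued until it is appropriate to transition the patient to a regimen of oral pain medications". For the control arm, section 3 says that "the intervention will include post-operative IV PCA with Hydromorphone" and gives a syringe strength and dose range, but no duration. Section 9 says that IV PCA includes a baseline infusion, so the reference to an IV infusion in the delirium schedule does apply to that arm.

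The list that begins "Data collection during 6-week follow-up visit (approximately postoperative 50 days" contains neither CAM nor Mini-Cog, although the delirium item schedules both at that visit.

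**The concern.** An incidence outcome that is found by repeated screening depends on how often one looks. Here the plan stops looking when the infusion stops, so the length of observation is set by the treatment under comparison. Nothing in the plan guarantees that the two arms are observed for the same time.

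Two consequences follow. First, the schedule does not cover the outcome as named: delirium that first appears after the infusion ends but before discharge has no scheduled check. Second, if infusion lengths differ by arm, a difference in detected delirium could arise from the schedule alone. Delirium bears on the relative safety of the two techniques, and checks that were not done cannot be recovered at analysis. Section 14 names no delirium analysis, denominator or adjustment for the number of assessments that might repair this.

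**Working it through.** **No plan figure to reproduce.** The documents give no delirium rate, power or test for this outcome. What follows is an illustration under stated assumptions.

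**Inputs from the protocol**
- 29 patients per arm (section 3).
- Epidural: 72 hours on the fixed statement, hence k = 3 daily checks. On the flexible statement, k is not fixed.
- IV PCA: duration not stated, so k = 1, 2 and 3 are each tried.

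**Assumptions**
- The daily probability p of a positive CAM is the same in both arms. I use 2%, 5% and 10%.
- Days are independent.

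**Formula.** P(at least one positive check) = 1 − (1 − p)^k.

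At p = 0.05:
- k = 3: 1 − 0.95³ = 14.26%
- k = 2: 1 − 0.95² = 9.75%
- k = 1: 5.00%

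Apparent risk ratios with three checks in one arm:
- 3 v 3: 14.26 / 14.26 = 1.0
- 3 v 2: 14.26 / 9.75 = 1.46
- 3 v 1: 14.26 / 5.00 = 2.85

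If the other arm has the longer infusion, the ratios invert: 9.75 / 14.26 = 0.68 and 5.00 / 14.26 = 0.35.

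Expected detected cases among 29 patients at p = 0.05 are 4.1 (k = 3), 2.8 (k = 2) and 1.5 (k = 1).

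| Daily risk | 3 checks | 2 checks | 1 check | Ratio 3 v 2 | Ratio 3 v 1 |
|---|---|---|---|---|---|
| 2% | 5.9% | 4.0% | 2.0% | 1.5 | 2.9 |
| 5% | 14.3% | 9.8% | 5.0% | 1.46 | 2.85 |
| 10% | 27.1% | 19.0% | 10.0% | 1.43 | 2.71 |

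**Chance of a nominally significant difference with no true difference in daily risk.** This uses a two-sided Fisher test at 0.05 with 29 per arm, by exact enumeration. The choice of test is mine, since the protocol names none.

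| Daily risk | 3 v 3 | 3 v 2 | 3 v 1 |
|---|---|---|---|
| 2% | 0.2% | 0.2% | 0.4% |
| 5% | 1.5% | 2.4% | 7.1% |
| 10% | 2.5% | 6.2% | 26.0% |

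The 3 v 3 column is the test's ordinary false-positive rate. A two-day window against three adds little to it. Only a large gap in duration combined with a high daily risk makes a spurious significant result likely. The distortion of the estimate is present whenever the windows differ.

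**After the fix.** With three checks in both arms the expected proportions are equal at every p (5.9%, 14.3% and 27.1% respectively), so the artefact is zero.

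**The case against.** A reader might infer that IV PCA stops sooner than a 72-hour epidural, so that the epidural arm gets more chances of a positive CAM and the bias runs against it. The documents do not support that. No section says how long IV PCA runs. Section 4 lists IV opioid use for postoperative days 1 to 3, and VAS at 24, 48 and 72 hours described as infusion days, without distinction by arm. Both are compatible with IV PCA also running to 72 hours. On that reading, daily checks during infusion already amount to a common three-day schedule.

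The epidural is not firmly fixed either. It may end when oral medication is judged appropriate. A failed catheter may be removed and the patient moved to IV PCA, with analysis primarily by intention to treat. Any imbalance could run in either direction.

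These objections stand, and they rule out any claim that following the plan must produce a difference or that its direction is known. The larger ratios above also depend on an IV PCA length of one day, which is only an assumption.

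What they do not remove is the rule itself. Equal windows are possible under the plan but not required by it. Section 4 also treats the last infusion day and postoperative day 3 as alternatives when timing the satisfaction score, with a further provision "at discharge if patient discharged before POD3". That item is not about delirium, but it shows that infusion length and stay are expected to vary. By contrast, nausea, vomiting and antiemetic use are given a fixed 72-hour window unrelated to infusion.

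The 6-week omission is clerical: the delirium item does schedule that check, in both arms alike, and a shorter list elsewhere does not cancel it.

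**Conclusion.** The concern holds as a defect of definition. In-hospital ascertainment of delirium is tied to a treatment-linked duration that is unstated in one arm and inconsistently described in the other, and the schedule is narrower than the outcome's name. If infusion lengths differ between arms, detected delirium can differ at equal daily risk. At an assumed 5% per day with independent days, the apparent ratio is 1.46 for three days against two and 2.85 for three against one. It is 1.0 if the lengths match, and falls below 1 if the difference runs the other way.

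Confidence is high that the window is undefined. The existence, size and direction of any imbalance cannot be settled from the documents. Delirium is one of many listed variables and plays no part in the sample size, so this is a worthwhile, inexpensive improvement rather than a threat to the trial's main conclusion.

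**What to change.** In section 4, replace the infusion-based wording with CAM and Mini-Cog at 24, 48 and 72 hours after surgery, or until discharge if that comes first, in both arms and whether or not the infusion is still running.

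Rename the outcome as delirium within 72 hours or to discharge, so that name and window agree. If delirium over the whole stay is what is wanted, continue daily checks to discharge in both arms instead. A 72-hour schedule under the present name would still miss later days.

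In section 14, state that the arms are compared over that common window, give the denominator, and report the number of assessments per patient by arm.

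Two tidying changes belong with this: add CAM and Mini-Cog to the 6-week list, and reconcile the two statements of epidural duration in section 3. The delirium schedule should not depend on how the latter is resolved.

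The cost is a wording change and a few extra brief bedside assessments in patients whose infusion has ended. Pain scores are already due at 24, 48 and 72 hours, so the added burden should be small. It is not nil if visits currently cease when the infusion does. No additional patients are needed.
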